1. OBJECTIVES

1.1 Primary Objectives

To determine the disease control rate (DCR) at 4 months using Response Evaluation Criteria for Solid Tumors (RECIST 1.1) in subjects with previously treated unresectable or metastatic adenosquamous pancreatic or ampullary cancer (ASQ) treated with retifanlimab.

1.2 Secondary Objectives

- 1.2.1 To determine the objective response rate (ORR) using RECIST 1.1.
- 1.2.2 To assess progression-free survival (PFS).
- 1.2.3 To characterize the treatment-related adverse events attributable to retifanlimab.

1.3 Exploratory Objectives

- 1.3.1 To assess overall survival (OS).
- 1.3.2 To assess duration of response (DOR) and time to progression (TTP).
- 1.3.3 To assess the DCR, ORR, PFS, and DOR by immune RECIST (iRECIST).
- 1.3.4 To identify potential biomarker predictors of response versus resistance to retifanlimab and autoimmune toxicity in plasma samples.
- 1.3.5 To test for predictors of response and resistance and explore changes in the tumor microenvironment (TME) following retifanlimab treatment in collected archived tissue and pre- and post-treatment biopsies via immunohistochemical studies.
- 1.3.6 Measure tumor marker kinetics (CA 19-9) in subjects receiving treatment and correlate with OS, PFS, and best overall response.
- 1.3.7 Measure tumor mutation burden, microsatellite instability, and profile genetic abnormalities in treated patients and correlate with response and resistance to therapy.

1.4 Study Design

This is multi-center two stage phase 2 study to evaluate the clinical activity of retifanlimab in patients with unresectable or metastatic ASQ. This study will enroll subjects who have progressed after at least 1 prior chemotherapy regimen, have been deemed unfit for cytotoxic chemotherapy or who have refused cytotoxic chemotherapy. The primary endpoint of this study will be disease control rate (DCR) at 4 months following the start of treatment using RECIST 1.1. Up to 25 subjects will be enrolled to target 21 evaluable patients.

The study will consist of a screening period (within 21 days of first dose), a treatment period per the table below (**Section 10**), and a follow-up period. Subjects will receive a baseline biopsy and then be treated with the anti-PD1 antibody retifanlimab every 4 weeks. After 2 doses (8 weeks), subjects will be assessed for response with imaging and laboratory tests and receive another research biopsy. For patients with stable disease or tumor response and clinical benefit, retifanlimab will be continued until disease progression or unacceptable toxicity. Patients will be evaluated radiographically after every 2 doses of retifanlimab (every 8 weeks). Subjects will come

to the clinic for dosing and assessments on Day 1 of each cycle. Assessment will consist of 1) physician evaluation to assess symptoms of tumor response or progression and potential drug related toxicity, 2) cross sectional imaging (CT scans), 3) CA19-9 blood levels. Additional visits for safety and immune monitoring follow-up will occur per the study calendar in **Section 10**.

No dose escalations or reductions are allowed. Enrollment will continue until 21 subjects have received at least one dose of retifanlimab and completed one cycle of therapy. The null hypothesis that the DCR 4 months following the start of treatment is 5% will be tested against a one-sided alternative (DCR of 30%).

Complete unacceptable toxicity criteria can be found in **Section 5.7**. At the investigator's discretion, subjects may receive additional cycles of treatment if they are clinically stable and meet dosing eligibility criteria. All subjects may continue in the treatment period until the criteria in **Section 5.9** are met. Subjects may continue on treatment with radiographic disease progression if clinically stable and investigator believes the treatment is providing benefit. Subjects will be considered in the treatment period until 28 days after the last dose of study drug.

Patients who have a confirmed complete response by two scans ≥ 4 weeks apart and who have been on retifanlimab treatment for at least 6 months may discontinue retifanlimab treatment at the discretion of the investigator after receiving at least two doses beyond the initial determination of CR. Patients with SD, PR or CR that received at least 24 months of retifanlimab may also discontinue retifanlimab at the discretion of the investigator. Retifanlimab may be resumed upon disease recurrence or progression in these patients. Criteria and procedures for retreatment are described in Sections 5.9.2 and 10.0.

After completion of treatment and end of treatment (EOT) visit assessments, all subjects, including those who did not receive treatment, will continue to be followed every three months (± 2 weeks) by telephone, e-mail, or optional clinic visit until death, withdrawal of consent, or closure of study. Subjects will also be contacted at 90 days (+14 day reporting window) from the last dose of therapy. Information on survival and new cancer therapies will be collected. All subjects who discontinue study treatment should continue to be monitored for disease status by radiologic imaging every two months (± 2 weeks) until: 1) the start of a new antineoplastic therapy (information of the new cancer therapy will be collected), 2) disease progression, 3) death, 4) withdrawal of consent, or 5) the close of the study, whichever occurs first. All subjects will be followed after their last dose of study drug for the development of adverse events (AEs) and serious adverse events (SAEs) as described in **Section 7.5**.

The primary analysis will be conducted 4 months after the last enrolled subject begins treatment, or all patients have either come off study or have completed 4 months on study. Information on survival may continue to be gathered for supplementary analyses after the completion of the primary analysis.

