- 4: Blood pressure, pulse, and temperature are required as indicated. Weight and pulse oximetry will be obtained at baseline and prior to each cycle. Height will be taken at or prior to screening only. Retifanlimab vitals will be collected prior to and at the end of the infusion (-5/+ 15 minutes).
- 5: Clinical hematology: CBC with differential ANC, ALC, AEC, and platelet count; Serum chemistry: sodium, potassium, chloride, bicarbonate, glucose, BUN, creatinine, ALT, AST, alkaline phosphatase, total bilirubin, direct bilirubin, lipase, total protein, albumin, calcium, magnesium, and phosphate. LDH at baseline only. Any unexpected Grade 3 or greater laboratory abnormalities should be repeated within 24-72 hours. Grade 3 or greater creatinine, AST, ALT, and bilirubin should be repeated within 24-72 hours as well.
- 6: TSH (Total T3 and free T4 if TSH abnormal and clinically indicated).
- 7: Bilirubin, blood, glucose, ketones, leukocytes, nitrite, pH, color, protein, RBC and WBC count, and specific gravity.
- 8: Virology screen: HIV antibody, hepatitis B surface antigen and hepatitis C antibody; additional virology may also be evaluated. Subjects who are hepatitis C antibody positive and confirmed negative viral load at screening will be allowed to enroll. Window for viral screen is -60 days to D1.
- 9: Coagulation panel: international normalized ratio of prothrombin time, APTT
- 10: Pregnancy tests will be administered to WOCBP: serum pregnancy test is required at screening; urine pregnancy tests are required before each dose of retifanlimab.
- 11: Labs may be collected within a window of up to 3 days prior to dosing.
- 12: ECG should be performed at baseline.
- 13: Spiral CT of thorax, abdomen and pelvis (and other imaging studies as clinically indicated to evaluate suspected sites of metastatic disease). If a subject cannot have a CT scan (e.g., allergy to contrast dye), an MRI should be performed. 3-D CT scans and RECIST reads will not be used to determine eligibility at baseline. On study radiologic evaluations and tumor measurements (RECIST and iRECIST per **Appendix B** and **Appendix C**) will be performed every 8 weeks (± 1 week; starting from the date of first treatment) including the EOT evaluation (± 4 weeks). If the EOT visit occurs early, scans do not need to be repeated if one has been done within the past 6 weeks. Weeks are in reference to calendar week and should not be adjusted due to dosing delays.

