11. STUDY ENDPOINTS

11.1 Primary Endpoint

The primary endpoint is DCR at 4 months following the start of treatment with retifanlimab, which is defined as the proportion of subjects with PR or CR or stable disease according to RECIST 1.1 following 4 months from the start of therapy. Subjects who discontinue due to toxicity prior to post-baseline tumor assessments will be evaluable and considered treatment failures. Otherwise, subjects who discontinue or do not have any post-baseline scans for other reasons including withdrawal of consent or being lost to follow-up prior to C2D1 will be replaced and not included in the primary efficacy analysis.

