13. STATISTICAL CONSIDERATIONS

13.1 Study Design/Endpoints

Sample Size calculation and justification

Simon's two-stage optimal design will be used ¹⁸. The null hypothesis that the true disease control rate at 4 months is 5% will be tested against a one-sided alternative of 30% disease control rate at 4 months. In the first stage, 7 patients will be accrued. If there are zero patients with disease control by 4 months, the study will be stopped. Otherwise, 14 additional patients will be accrued for a total of 21 patients. The null hypothesis (disease control rate of 5%) will be rejected if 3 or more patients with disease control at 4 months are observed in stage 1 and 2 combined. This design yields a type I error rate of 0.064 (target type I error 0.1) and power of 90% when the true disease control rate is 30%. The probability of stopping the trial early for futility is 70% if the true DCR is 5%.

We plan to enroll 25 subjects to ensure 21 would be evaluable for DCR. As this is a rare tumor subtype patients will be recruited at several sites including Johns Hopkins Hospital, Memorial Sloan Kettering Cancer Center and the Mayo Clinic. We do not anticipate any difficulties in trial enrollment. We expect an accrual rate of at least 2 patients per month across the sites, completing trial enrollment in 12 months.

Patients are evaluable for DCR if they receive at least one dose of retifanlimab, and have at least one post-baseline tumor assessments or discontinue due to toxicity or clinical progression prior to post-baseline tumor assessments. The study plans to enroll 25 subjects to ensure 21 would be evaluable for the primary efficacy endpoint.

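### Section 1.4 closes enrolment on 21 subjects who completed one cycle, which conflicts with the plan's own target of 21 subjects evaluable for DCR and can leave the trial slightly short

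*Combined protocol and SAP*

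**What the plan says.** Four places bear on who makes up the 21.

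- **Closing rule (Section 1.4):** "Enrollment will continue until 21 subjects have received at least one dose of retifanlimab and completed one cycle of therapy". The same section also sets a ceiling of 25 enrolled with a target of 21 evaluable.
- **Evaluability (Section 13.1):** "Patients are evaluable for DCR if they receive at least one dose of retifanlimab, and have at least one post-baseline tumor assessments", or if they stop for toxicity or clinical progression before any such assessment. This section says twice that 25 are enrolled so that 21 are evaluable.
- **Replacement (Section 11.1):** toxicity stops before a scan count as failures. Subjects who stop, or have no post-baseline scan, for other reasons are covered by a clause ending "withdrawal of consent or being lost to follow-up prior to C2D1 will be replaced and not included in the primary efficacy analysis".
- **Scan timing (Section 10, footnote 13):** imaging "will be performed every 8 weeks (± 1 week; starting from the date of first treatment". Section 5.1 gives a 28-day cycle, so C2D1 is about week 4 and the first scheduled scan falls about four weeks later.

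The design in Section 13.1 is a Simon two-stage test of a 5% null DCR at 4 months against a one-sided 30% alternative. Stage 1 takes 7 patients, with this futility rule: "If there are zero patients with disease control by 4 months, the study will be stopped". If the trial continues, stage 2 adds 14, and rejection needs at least 3 successes among the 21. The stated properties are type I error 0.064, power 90% and a 70% chance of early stopping under the null.

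**The concern.** The count that closes accrual is reached about four weeks before a subject can normally become evaluable by scan. Take a subject who completes cycle 1, then withdraws consent or is lost, and is never scanned. That subject counts toward the 21 in Section 1.4 and is not evaluable under Section 13.1. Whether a replacement is enrolled depends on how Section 11.1 is parsed. The C2D1 limit may govern the whole clause, in which case there is no replacement, or only the loss-to-follow-up example, in which case a withdrawal at week 6 would be replaced.

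The stated power belongs to 7 then 21 evaluable patients. If the test is run on fewer with the same threshold of 3, power falls. A stage 1 loss costs most, because that stage stops on zero successes. The primary denominator of a 21-patient trial should also not depend on which of two sentences in one section a site follows.

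**Working it through.** **Inputs.** From Section 13.1: null 5%, alternative 30%, stage 1 of 7 (stop on 0), stage 2 of 14, reject on at least 3 in total, and 25 enrolled for 21 evaluable. The week 4 to 8 loss rate is not given, so values below are assumed.

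**Formula.** With n1 in stage 1 and n2 in stage 2, the null is not rejected if X1 = 0, or X1 = 1 and X2 ≤ 1, or X1 = 2 and X2 = 0. Hence

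P(reject) = 1 − [P(X1=0) + P(X1=1)·P(X2≤1) + P(X1=2)·P(X2=0)].

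**Step 1: the plan's own figures (n1 = 7, n2 = 14).**

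- At 30%: 1 − [0.08235 + 0.24706 × 0.04748 + 0.31765 × 0.00678] = 0.9038.
- At 5%: 1 − [0.69834 + 0.25728 × 0.84701 + 0.04062 × 0.48767] = 0.0639.
- Early stop under the null: 0.95^7 = 0.698.

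All three stated figures reproduce.

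**Step 2: fewer evaluable, threshold of 3 unchanged.**

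| Evaluable (stage 1, total) | Power at 30% | Type I error at 5% | Futility stop at 30% |
|---|---|---|---|
| 7, 21 | 0.904 | 0.0639 | 8.2% |
| 7, 20 | 0.899 | 0.0584 | 8.2% |
| 7, 19 | 0.892 | 0.0529 | 8.2% |
| 7, 18 | 0.883 | 0.0475 | 8.2% |
| 6, 20 | 0.866 | 0.0534 | 11.8% |

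The last row has one loss in stage 1: 1 − [0.7^6 + 0.30253 × 0.04748 + 0.32414 × 0.00678] = 1 − [0.11765 + 0.01436 + 0.00220] = 0.866.

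**Step 3: how likely a shortfall is, under assumed loss rates.** Let each of 21 cycle-1 completers be lost unscanned with probability q, in either stage, without replacement. The expected loss is 21q, the chance that none is lost is (1 − q)^21, and power is the Step 1 formula at 0.30(1 − q).

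| q (assumed) | Expected lost | P(all 21 evaluable) | Power |
|---|---|---|---|
| 5% | 1.05 | 34% | 0.886 |
| 10% | 2.1 | 11% | 0.864 |

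The rejection rule is an absolute count, so this power is the same whether a lost subject is dropped or scored as a failure.

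**Step 4: closing on evaluable subjects.** This restores the first row of Step 2. If each of 25 enrolled is non-evaluable with assumed probability 5% or 10%, the chance of at least 21 evaluable is 99.3% or 90.2%.

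**The case against.** Four points can be made for the plan.

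1. **The target is stated correctly elsewhere.** Sections 1.4 and 13.1 both aim for 21 evaluable out of 25. This stands against any claim that the design will not be delivered. The shortfall arises only if the one-cycle sentence prevails. It does not remove the conflict, because that sentence is the only one in Section 1.4 that says when accrual ends.
2. **Section 11.1 may already replace these subjects.** Its clause covers those without a post-baseline scan for other reasons, and the word that introduces withdrawal and loss marks them as examples. A reader might infer that anyone lost in weeks 4 to 8 is neither replaced nor evaluable. The text does not establish that; it leaves replacement open.
3. **The affected group is narrow.** Toxicity and clinical-progression stops are evaluable under Section 13.1 without a scan. A subject who stops treatment but stays in the study is due an end-of-treatment CT 28 days ± 4 weeks after the last dose (Section 10, footnotes 13 and 20) and can become evaluable that way. What remains is mainly full withdrawal of consent, loss to follow-up, or another departure with no scan at all.
4. **The effect is small.** This stands for stage 2 losses, where one or two cost 0.5 to 1.2 percentage points. It is weaker for stage 1, where a single loss costs about 4 points (0.904 to 0.866).

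**Conclusion.** The closing rule in Section 1.4 conflicts with the evaluability target in the same section and with Section 13.1, and the replacement rule in Section 11.1 is ambiguous for a subject who leaves unscanned after C2D1. If the one-cycle sentence is followed, fewer than 21 may be evaluable. Power then falls from 0.904 to between 0.899 and 0.883 for one to three stage 2 losses, and to 0.866 for one stage 1 loss, with the false futility stop rising from 8.2% to 11.8%. Type I error falls in every such case, so a reader who inferred a false-positive risk from the shortfall would be mistaken.

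These sizes assume the threshold of 3 is kept and lost subjects are not replaced. How many would be lost in weeks 4 to 8 cannot be taken from the documents. The 4-in-25 allowance shows only that some non-evaluable subjects are expected. Severity: minor.

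**What to change.** 1. **Section 1.4.** Replace the one-cycle sentence with wording such as: *Accrual closes once 21 subjects (7 in stage 1) are evaluable for DCR under Section 13.1, with no more than 25 enrolled.* The stage 1 count matters because a loss there costs most.
2. **Section 11.1.** Reconcile the replacement clause with the Section 13.1 definition and state plainly what C2D1 limits. Do not narrow the clause to withdrawal and loss alone, since subjects who leave unscanned for other reasons would then be neither evaluable nor replaceable. At the same time settle clinical progression before a scan, which Section 13.1 treats as evaluable and Section 11.1 does not name.
3. **Section 13.2.** Add a sensitivity analysis of DCR in all treated subjects, with unscanned subjects counted as failures. Section 13.1 cites a median PFS of 1.5 months with checkpoint inhibition in PDAC, so subjects who leave in weeks 4 to 8 may be early failures, and replacing them can raise the observed DCR. As an extreme case, suppose all 4 of the allowed non-evaluable subjects are true failures and the DCR among all 25 is 5%. The rate among the evaluable is then 5% × 25/21 = 5.95%, and the Step 1 formula at that rate gives a rejection probability of 0.096, against 0.064 stated and a target of 0.1. The same 3 successes would read as 3/21 = 14.3% in the primary analysis and 3/25 = 12.0% in the sensitivity analysis.

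**Cost.** Wording in three sections and one extra table, within the 25 subjects already planned. Accrual may be declared complete about four weeks later, at the week 8 scan.

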2. BACKGROUND

2.1 Study Disease

Pancreatic cancer is estimated to be the second leading cause of cancer-related death in the US by 2030¹. It is one of the deadliest cancers – it has the lowest 5 year survival rate of all cancer types with most patients being diagnosed with advanced disease with a median survival less than 1 year². In unresectable and metastatic patients standard regimens only include cytotoxic chemotherapy. As far as single agents – gemcitabine reports a median survival of 5.65 to 6.8 months and overall tumor response rates are 5.4 to 9.4% ³. To achieve reasonable response rates multiagent regimens are utilized. The FOLFIRINOX regimen utilizes a combination of oxaliplatin, irinotecan, fluorouracil, and leucovorin. Response rates are 31.6% and estimated median OS is 11.1 months⁴. Another established combination regimen is *nab*-paclitaxel combined with gemcitabine with ORR of 23% and median OS of 8.5 months⁵. As expected these multiagent cytotoxic regimens cause significant toxicity and are often reserved for the fittest patients. This trial involves a targeted approach to treating a subtype of pancreatic adenocarcinoma with the goal to establish immunotherapy in this deadly disease.

ASQ of the pancreas constitutes 1 to 5% of all pancreatic cancers and compared to pancreatic adenocarcinoma has a worse survival. ASQs have glandular and squamous histologic components (>30% squamous component for the diagnosis) and are considered a variant of pancreatic ductal adenocarcinomas. Given its rarity and aggressiveness, systemic therapy has not been well studied in ASQ and in practice a cytotoxic chemotherapy treatment paradigm is pursued in advanced disease with overall poor outcomes⁶. In addition, there is no data regarding the efficacy of immune checkpoint inhibition in ASQ pancreatic cancer, and most clinical trials have excluded them from eligibility.

2.2 Rationale

Immunotherapies in Pancreatic Cancer

Pancreatic ductal adenocarcinoma (PDAC) is considered an immune quiescent tumor and single agent checkpoint blockade has had an overall disappointing impact on survival (including targeting PD-1, PD-L1 and CTLA-4)⁷⁻⁹. Immunotherapeutic approaches have shown some ability to "reprogram" the immune tumor microenvironment (TME) within pancreatic tumors¹⁰⁻¹². Several studies have also described the clinical and prognostic significance of PD-L1 expression in pancreatic cancer including higher expression levels predicting a poor prognosis further suggesting the immune TME influences pancreatic tumor behavior¹³⁻¹⁵. In an effort to identify patient subgroups most likely to respond to immunotherapy, the immune TME in the rare pancreas cancer histological subtype - adenosquamous carcinoma (ASQ) was evaluated by our team. Indeed a recent article reported high PD-L1 expression in a series of ASQ cases (5 of 6 surgical cases)¹⁶.

Tumor microenvironment of adenosquamous pancreatic cancer subtype

Retifanlimab and its dose selection

Hypothesis

Retifanlimab treatment will have clinical activity in patients with ASQ, a subtype of pancreatic and ampullary cancer that has a dynamic tumor microenvironment.

3. PATIENT SELECTION

3.1 Inclusion Criteria

- 3.1.1 Age \geq 18 years.
- 3.1.2 Have histologically- or cytologically-proven adenosquamous carcinoma of the pancreas or ampulla by pathologic review. Patients must have squamous component to be included. All pathology will be reviewed by Johns Hopkins or Cedars-Sinai Department of Pathology.
- 3.1.3 Have unresectable or metastatic disease.
- 3.1.4 Must have received (or been intolerant to, ineligible for, or refused) at least 1 prior line of cytotoxic chemotherapy and received no more than 2 prior systemic treatments.
- 3.1.5 Presence of at least one lesion with measurable disease as defined by 10 mm in longest diameter for a soft tissue lesions or 15 mm in short axis for a lymph node by RECIST 1.1.
- 3.1.6 Patient's acceptance to have a tumor biopsy of an accessible lesion at baseline and on treatment if the lesion can be biopsied with acceptable clinical risk (as judged by the investigator).
- 3.1.7 ECOG performance status 0 or 1 (**Appendix A**).
- 3.1.8 If HIV-positive, then all of the following criteria must also be met: CD4+ count \geq 350/ μ L, undetectable viral load, and receiving highly active antiretroviral therapy.
- 3.1.9 Life expectancy of greater than 3 months.
- 3.1.10 Adequate organ and marrow function as defined below:

 $\begin{array}{lll} - & Leukocytes & \geq 3,000/mcL \\ - & Absolute neutrophil count \\ - & Platelets & \geq 75 \times 10^3/uL \\ - & Hemoglobin & \geq 8.0 \text{ g/dL} \end{array}$

- Total bilirubin \leq upper limit of normal (ULN) except subjects with

Gilbert Syndrome, who can have total bilirubin <

3.0 mg/dL

AST(SGOT) and ALT(SGPT)≤2.5 × ULN
 Alkaline phosphatase ≤5.0 × ULN

- Creatinine $\leq 1.5 \times \text{ULN}$ or creatinine clearance (CrCl)

≥ 40 mL/min (if using the Cockcroft-Gault formula

below):

Female CrCl = $(140 - age in years) \times weight in kg \times 0.85$ 72 x serum creatinine in mg/dL

Male CrCl = (140 - age in years) x weight in kg x 1.0072 x serum creatinine in mg/dL

- Albumin $\geq 2.5 \text{ g/dL}$

- 3.1.11 Women of childbearing potential (WOCBP) must have a negative serum pregnancy test (minimum sensitivity 25 IU/L or equivalent units of human chorionic gonadotropin [HCG]). WOCBP is defined in **Section 5.7. NOTE:** If a patient has a positive or indeterminate serum or urine pregnancy test, then an ultrasound must be done to rule out pregnancy to enroll on trial.
 - WOCBP must agree to follow instructions for method(s) of contraception from the time of screening, through the duration of treatment with study drug plus 6 months after the last dose of study drug.
 - Men who are sexually active with WOCBP must agree to follow instructions for method(s) of contraception from the time of screening, through the duration of treatment with study drug plus 6 months after the last dose of study drug.
 - At least one barrier method of contraception must be employed by all sexually active patients (male and female), regardless of other methods, to prevent the transfer of body fluids.
- 3.1.12 Ability to understand and willingness to sign a written informed consent document.

